3.3.1.4 Handling of missing dates

Missing adverse event (AE) and concomitant medication (CM) start and end dates will be imputed as follows:

For partial or missing start dates:

- Missing day: impute the 1st of the month unless month is same as month of first dose of study drug then impute first dose date.
- Missing day and month: impute 1st January, unless the year is the same as first dose date and the end date does not suggest it could have started prior to first dose (i.e. end date is before first dose date), then impute first dose date.
- Completely missing: impute first dose date unless the end date suggests it could have started prior to this in which case impute the 1st January of the same year as the end date.

For partial or missing end dates:

- Missing day: impute the last day of the month unless month is same as month of first dose of study drug then impute last dose date.
- Missing day and month: impute 31st December unless year is the same as first dose date then impute last dose date.
- Completely missing: need to look at whether the AE or CM is still ongoing before imputing a date and also when it started in relation to study drug. If the ongoing flag is missing then assume that AE or CM is still present (i.e. do not impute a date). If the AE or CM has stopped and start date is prior to first dose date then impute the last dose date, if it started on or after first dose date then impute a date that is after the last dose date.

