Optional Prescreening procedures will be performed, using i-STAT (A portable blood analyser) potassium values, to determine the consenting patients eligibility to enter the screening phase at Visit 1. If i-STAT potassium value is <5.1 mmol/L the patient will be declared a pre-screen failure. Screening procedures will be performed to determine patient eligibility during the screening period, and all baseline parameters should be measured/collected up to 1 day prior to administration of first dose of study drug on the open-label initial phase. In the open-label initial

phase, patients will receive open-label ZS at a dose of 10g per os (PO) three times a day (tid) for 24 or 48 hours, depending on potassium value. Once normokalemia (i-STAT potassium between 3.5 and 5.0 mmol/L, inclusive) is restored (whether after 24 or 48 hours, i.e., by the morning of Study Day 2 or Day 3), patients will then be randomized in the ratio of 2:2:1 into the double-blind 28-day randomized treatment study phase to receive ZS 5g once daily (qd), 10g qd or placebo qd for the following 28 days. Treatment will end on Day 29 visit, which will be followed by the end of study (EOS) visit taking place 7 ± 1 days after the last administration of study medication.

For patients who do not enter the 28-day randomized treatment study phase, the last visit will be 7 ± 1 days after the last treatment dose in the open-label initial phase.

Objectives

Primary Objective:	Outcome Measure:
To evaluate the efficacy of two different doses (5 and 10 g) of ZS orally administered once daily (qd) for 28 days in maintaining normokalemia (serum potassium [S-K] between 3.5-5.0 mmol/L, inclusive) in normokalemic patients following treatment in the open-label phase for hyperkalemic patients (two consecutive i-STAT potassium values \geq 5.1 mmol/L, taken 60 minutes apart) at baseline.	Comparison between placebo and each ZS treatment group (high to low) with regard to the mean S-K level during the 28-day randomized treatment study phase Days 8-29.

Secondary Objectives:	Outcome Measures:

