8. Randomization Visit may occur for patients who achieve normokalemia on open-label initial phase Day 2 or 3.

Table 5Volume of blood to be withdrawn from each patient: 28-day randomized
treatment study phase

Assessment	Sample Volume (mL)	Numb	er of S	amples									Maxi mum blood volu me Total (mL)
		Rand D1 ²	V6 D2 ²	V7 D5 ²	V8 D8 ²	V9 D12 ²	V10 D15 ²	V11 D19 ²	V12 D22 ²	V13 D26 ²	V14 D29 ²	EOS D35 ²	
Hematology	2	1					1				1	1	8
Clinical Chemistry	8.5	1^1					1^{1}				1^{1}	1^1	34

Assessment	Sample Volume (mL)	ume											Maxi mum blood volu me Total (mL)
		Rand D1 ²	V6 D2 ²	V7 D5 ²	V8 D8 ²	V9 D12 ²	V10 D15 ²	V11 D19 ²	V12 D22 ²	V13 D26 ²	V14 D29 ²	EOS D35 ²	
Potassium (Central Lab S-K ¹)	2.5		1	1	1	1		1	1	1			17.5
Potassium (i- STAT)	1	1	1	1	1	1	1	1	1	1	1	1	11
Maximum Blood Volume Total (mL)		11.5	3.5	3.5	3.5	3.5	11.5	3.5	3.5	3.5	11.5	11.5	70.5

Table 5Volume of blood to be withdrawn from each patient: 28-day randomized
treatment study phase

V=Visit; D=Day

1. Potassium will be measured fasting prior to the daily dose. Central Laboratory S-K sample collected as part of the serum clinical chemistry at Day 1, 15, 29, and 35.

2. Study Day in Table 5 is day for the 28-day randomized treatment study phase.

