4.1.6.2 Presentation

Medical history and surgical history are grouped by MedDRA system organ class and preferred term and are summarized by System Organ Class (SOC) and Preferred Term (PT), for all subjects in FAS-OLP and in FAS-RTP.

They will be listed for all subjects enrolled and summarized respectively for the FAS-OLP and FAS-RTP. This listing will be presented sorted by treatment group, subject ID, and date/time of the event.

4.1.7 **Prior and Concomitant Medications**

4.1.7.1 **Definitions and Derivations**

Medications will be classified according to the latest version of the WHO Drug coding dictionary. Prior medication is any medication that started and stopped prior to treatment with investigational product. Concomitant medication is any medication that is taken concurrently with investigational product regardless of the start date of the medication. Concomitant medications include allowed and disallowed medications taken by the subjects during the respective phases (i.e. a medication can be concomitant for the OLP but not RTP, or RTP but not OLP). Missing medication start and stop dates will be imputed according to Section 3.3.1.4.

For the definition of disallowed medications, see Appendix B.

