4.2.1.5 Supplementary and Sensitivity Analyses of Primary Endpoint

A sensitivity analysis will be conducted to assess the potential discrepancy in observed effect as assessed through by c-lab potassium, as opposed to i-STAT. This will be performed by using the same longitudinal model as was used for the main analysis of the primary endpoint on subjects Day 8 to Day 29 i-STAT measurements.

A supplementary analysis, aimed at evaluating the impact of the usage of disallowed medications on the efficacy results, will also be conducted. This will be done by means of removing the potassium measurements that occurred while a subject was receiving a disallowed medication (between medications start date and stop date, plus 7 days), replacing them using a MI approach, and replicating the main analysis on each of the resulting data sets. See Section 4.2.1.3 for details on the MI procedure.

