7.2 Appendix B: Disallowed Medications

Disallowed medications in the study broadly consist of two classes: potassium binders and RAASi / diuretics. For the former, any use of while on IP is to be considered as an instance of disallowed medication usage. For the latter, as per the CSP, the addition of a new RAAS inhibitor and/or diuretic, or change of the dose, discontinuation, or switch of these drugs, is to be considered as an instance of usage of disallowed mediation.

The exact method by which such instances of usage can be identified in the database will be documented separately.

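### The SAP's missing-date rule can impute a stop date later than the recorded month or year, which distorts medication windows in the supplementary analyses

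*SAP*

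**What the plan says.** SAP 3.3.1.4 sets one group of rules for missing adverse event and medication dates, and SAP 4.1.7.1 applies them to medications: "Missing medication start and stop dates will be imputed according to Section 3.3.1.4".

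- **End date, day missing:** "impute the last day of the month unless month is same as month of first dose of study drug then impute last dose date".
- **End date, day and month missing:** 31 December, but the last dose date if the recorded year is the first-dose year.
- **Start date:** "Completely missing: impute first dose date unless the end date suggests it could have started prior to this". A start with only the month or only the year recorded also goes to the first dose date when that month or year matches first dose. For the year-only case this holds unless the end date precedes first dose.

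These dates are used later. The supplementary analysis of the primary endpoint (SAP 4.2.1.5) removes potassium values taken during disallowed medication, defined as "between medications start date and stop date, plus 7 days", and replaces them by multiple imputation. SAP 4.2.2.6 and 4.2.3.4 treat users of disallowed medication as non-responders in composite analyses. Appendix B counts any potassium-binder use while on study drug as disallowed. For the other class it lists "the addition of a new RAAS inhibitor and/or diuretic", as well as dose change, discontinuation and switch. It leaves the method of finding these instances to a separate document.

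**The concern.** An imputed date should agree with whatever part of the date was recorded. The end-date rule tests the month of first dose and then fills in the date of last dose, which for most completers lies in the next month. A short course that ended in the first-dose month is stretched to the end of dosing. A drug that stopped before first dose in that month becomes concomitant for the whole dosing period.

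The start-date rule carries a related risk. A long-standing RAAS inhibitor or diuretic with an unknown start, or with only the first-dose year recorded, is dated to first dose and can look newly added.

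The supplementary analyses exist to show how much disallowed medication matters. If date imputation creates or lengthens such use, they no longer answer that question cleanly.

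**Working it through.** The documents give no figure for this rule, so there is none to reproduce. The check applies the rule to the calendar.

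**Inputs.** Patients "receive ZS 5g once daily (qd), 10g qd or placebo qd for the following 28 days" (Protocol synopsis). On open-label timing, "Randomization Visit may occur for patients who achieve normokalemia on open-label initial phase Day 2 or 3" (Protocol 5.10). For a completer on schedule, last dose = randomization + 27 days. That is first open-label dose + 28 days (24-hour path) or + 29 days (48-hour path).

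**How often the imputed stop leaves the recorded month.** In a month of L days, a first dose on day d with last dose k days later crosses month end when d + k > L. That holds for min(k, L) of the L days. For 2021:

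| Dates used | k | Crossing first-dose dates | Share |
|---|---|---|---|
| Open-label first dose to randomized last dose, 24 h | 28 | 12 × 28 = 336 | 336/365 = 92.1% |
| Same, 48 h | 29 | 11 × 29 + 28 = 347 | 347/365 = 95.1% |
| Randomized-phase dates only | 27 | 12 × 27 = 324 | 324/365 = 88.8% |

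In the first two rows the imputed stop passes month end by 14.5 to 15.0 days on average (range 1 to 29).

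**Effect on one record.** First dose 20 March 2021, randomized 21 March, last dose 17 April. The seven Day 8–29 visits fall on 28 March and 1, 4, 8, 11, 15 and 18 April. Suppose a binder was in use by Day 8 and its stop is recorded only as March 2021.

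- Current rule: stop 17 April, window to 24 April, all 7 visits removed.
- Capped at month end: stop 31 March, window to 7 April, 3 visits removed (Days 8, 12, 15).
- If the true stop was 25 March: window to 1 April, 2 visits removed (Days 8, 12).

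Over all 2021 first-dose dates and both paths, weighted equally and with use in place by Day 8, the current rule removes 7.0 of 7 visits and the cap 4.2. If use is dated from randomization or earlier, the Day 2 and Day 5 values go too. The imputation model (SAP 4.2.1.3) then rests mainly on baseline covariates and treatment arm.

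**Year rule.** First dose 20 December 2021 on the 24-hour path gives last dose 20 December + 28 days = 17 January 2022. A stop recorded only as 2021 is imputed in 2022.

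**Stop before start.** Protocol 7.7 allows other hyperkalemia treatment once study drug has stopped. If first dose was 3 March, study drug stopped on 12 March, and a binder started on 14 March with its stop recorded as March, the rule imputes 12 March. That is before the drug began.

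**The case against.** The strongest reply is that the reach is narrow, and most of it stands.

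- **Confirmatory results.** A reader might infer that these are at risk. They are not. The main analysis of the primary endpoint and the main secondary analyses ignore intercurrent events (SAP 4.2 and 4.2.1.1). SAP 3.3.7 treats tests outside the hierarchy as exploratory.
- **Binders stopped before first dose.** Exclusion criterion 6 bars listed binders within 7 days before first dose, and Protocol 7.7 records medications from 7 days before open-label Day 1. Such a record should be uncommon. If the binder stopped after first dose, use on study drug was real and non-responder status is correct; only the window is too long.
- **New RAAS inhibitor or diuretic.** A reader might infer that false additions are certain. The documents show only a risk, because Appendix B defers identification to a document not available here. A drug whose recorded month or year precedes first dose is not affected.
- **Deviation counts.** A reader might infer that these are wrong too. Appendix A finds RAAS-inhibitor and diuretic changes by source data review. It finds prohibited medication by physician and source review as well as programming. SAP 3.3.8 excludes nobody for a deviation.
- **Adverse events.** On-treatment status and phase depend on onset (SAP 3.3.1.2 and 4.3.2.2), so an imputed end date affects duration only.
- **Percentages.** They describe the calendar, not the number of affected patients. They assume a completer and a stop recorded in the first-dose month. SAP 3.3.1.4 does not say which phase's doses it means; with open-label dates only, the overshoot is about a day. The roughly 280 − 250 = 30 patients not expected to be randomized fall outside the calculation.

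None of this defends an imputed date that contradicts the recorded one.

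**Conclusion.** The end-date rule is wrong as written. For completers with a day-missing stop in the first-dose month, it gives a date outside that month for 92% to 95% of possible first-dose dates, or 89% on randomized-phase dates. The year rule fails in the same way across a year end.

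The consequences are limited to longer disallowed-medication windows in the supplementary primary analysis, some prior drugs classed as concomitant in the medication summaries, and possibly the composite supplementary analyses. The error can also run the other way: a RAAS inhibitor or diuretic truly stopped early in the first-dose month has its discontinuation moved to the end of dosing. The total effect cannot be sized, because the number of partial dates is not given.

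The start-date rule can misplace a long-standing drug in the prior/concomitant timeline. Whether that creates a disallowed-medication flag depends on the separate identification document.

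**What to change.** 1. In SAP 3.3.1.4, where the recorded month (or year) is that of first dose, impute the earlier of the last day of that month (or year) and the last dose date, and never a date before the recorded start.
2. State whether first and last dose mean the open-label or the randomized phase.
3. In Appendix B or the identification document, state that an imputed start date alone does not count as adding a new RAAS inhibitor or diuretic. This is safer than assuming that every unknown start precedes first dose, which would hide some genuine additions.

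The cap does not settle whether a drug recorded as stopped in the first-dose month ended before first dose. Those records still need a look in the medical review that SAP 4.1.7.2 already allows for.

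The cost is a few lines of text and a small programming change. No new data are needed and no confirmatory analysis changes.

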3.3.2 Hypotheses

3.3.2.1 Primary hypotheses

Endpoint: Mean S-K level between placebo and each ZS treatment group (high to low) during the 28-day randomized treatment study phase Days 8-29.

The null hypothesis: No treatment difference in the mean S-K levels during RTP (Days 8-29) compared to placebo as follows (two null hypotheses):

For this endpoint the null hypothesis is that during RTP (Days 8-29) there is no treatment difference in the mean S-K levels; and the alternative is compared to placebo there is a difference in the mean S-K levels:

$$H_{0}: \mu_{sk}(ZS_{10g}) = \mu_{sk}(Placebo) \text{ vs. } H_{A}: \mu_{sk}(ZS_{10g}) \neq \mu_{sk}(Placebo)$$
$$H_{0}: \mu_{sk}(ZS_{5g}) = \mu_{sk}(Placebo) \text{ vs. } H_{A}: \mu_{sk}(ZS_{5g}) \neq \mu_{sk}(Placebo)$$

3.3.2.2 Secondary hypotheses

For the OLP, the following hypotheses will be tested versus two-sided alternatives:

Endpoint: Exponential rate of change in S-K levels (blood) at 24 hours and 48 hours during OLP.

The null hypothesis:

$$H_0$$
: Exponential rate A_{S-K} (24 hours) = 0 vs. H_A : Exponential rate A_{S-K} (24 hours) $\neq 0$

 H_0 : Exponential rate $\Delta S-K$ (48 hours) = 0 vs. H_A : Exponential rate $\Delta S-K$ (48 hours) $\neq 0$

This is evaluated by the parameter estimate of time (in hours) from a mixed effects model as described in Section 4.2.2.4. Note that the exponential rate of change refers to the degree of decline in SK values over time, which is assumed to follow an exponential trend.

Endpoint: Mean change (absolute and percent (%) change) from baseline in S-K levels

The null hypotheses:

$$H_0: \mu_{\Delta S-K} (24 \text{ hours}) = 0 \text{ vs. } H_A: \mu_{\Delta S-K} (24 \text{ hours}) \neq 0$$
$$H_0: \mu_{\Delta S-K} (End \text{ of } OLP) = 0 \text{ vs. } H_A: \mu_{\Delta S-K} (End \text{ of } OLP) \neq 0$$

The end of OLP can be 24 or 48 hours depending on the duration of OLP, as subjects who did not achieve normokalemia at 24 hours are evaluated again at 48 hours.

There will be a similar hypothesis for the mean percent change of S-K at 24 and 48 hours.

For the RTP, the following hypotheses will be tested:

Endpoint: Proportion of subjects who remain normokalemic at the end of the RTP and during the RTP.

The null hypotheses:

$$H_0: OR \left(ZS_{10g} vs Placebo \right) = 1. vs. H_A: OR \left(ZS_{10g} vs Placebo \right) \neq 1$$
$$H_0: OR \left(ZS_{5g} vs Placebo \right) = 1. vs. H_A: OR \left(ZS_{5g} vs Placebo \right) \neq 1$$

For each of the treatment arm comparisons, two tests will be done: one aiming at evaluating the odds of being normokalemic Day 8-29, performed by means of a generalized random effects model as described in Section 4.2.3, and another aiming at evaluating the probability of being normokalemic at Day 29 in particular, performed by means of a logistic regression model.

Endpoint: Number of days subjects remain normokalemic during the RTP.

The null hypotheses:

 $H_0: \mu_{\text{days of normokalemic}}(ZS_{10g}) = \mu_{\text{days of normokalemic}}(Placebo) \text{ vs.}$ $H_A: \mu_{\text{days of normokalemic}}(ZS_{10g}) \neq \mu_{\text{days of normokalemic}}(Placebo)$

 $H_0: \mu_{\text{days of normokalemic}}(ZS_{5g}) = \mu_{\text{days of normokalemic}}(Placebo) \text{ vs.}$ $H_A: \mu_{\text{days of normokalemic}}(ZS_{5g}) \neq \mu_{\text{days of normokalemic}}(Placebo)$

Endpoint: Time to hyperkalemia.

The null hypotheses:

$$H_{0}: HR \left(ZS_{10g} vs Placebo \right) = 1. vs. H_{A}: HR \left(ZS_{10g} vs Placebo \right) \neq 1$$
$$H_{0}: HR \left(ZS_{5g} vs Placebo \right) = 1. vs. H_{A}: HR \left(ZS_{5g} vs Placebo \right) \neq 1$$

Endpoint: The mean changes in S-Aldo and P-Renin levels during RTP

The null hypotheses:

$$\begin{aligned} H_{0}: \mu_{Aldo}(ZS_{10g}) &= \mu_{Aldo}(Placebo) \text{ vs. } H_{A}: \mu_{Aldo}(ZS_{10g}) \neq \mu_{Aldo}(Placebo) \\ H_{0}: \mu_{Aldo}(ZS_{5g}) &= \mu_{Aldo}(Placebo) \text{ vs. } H_{A}: \mu_{Aldo}(ZS_{5g}) \neq \mu_{Aldo}(Placebo) \\ H_{0}: \mu_{Renin}(ZS_{10g}) &= \mu_{Renin}(Placebo) \text{ vs. } H_{A}: \mu_{Renin}(ZS_{10g}) \neq \mu_{Renin}(Placebo) \\ H_{0}: \mu_{Renin}(ZS_{5g}) &= \mu_{Renin}(Placebo) \text{ vs. } H_{A}: \mu_{Renin}(ZS_{5g}) \neq \mu_{Renin}(Placebo) \end{aligned}$$

3.3.3 Visit Window

In the absence of nominal visits, visits windows will apply. Measurements will be assigned to exhaustive visit windows based on study day such that measurements taken at any time point can be accounted for and used in summaries and/or analyses. If an unscheduled visit occurred in the same window, then the measurement from the scheduled visit will be used in the analysis. If there are multiple unscheduled visits in the same visit window, then the visit closest to the scheduled visit day will be used. If there are multiple records on the same day the last measurement will be used.

- For summaries showing the maximum or minimum values, the maximum/minimum value recorded on treatment is used (regardless of where it falls in an interval).
- Listings display all values contributing to a time point for a subject.
- For visit-based summaries
 - If there is more than one scheduled value per subject within a time window then the closest value to the scheduled visit date is summarized. If the scheduled values are equidistant from the nominal visit date, then the earlier value is used. Data listings will highlight the values used in the summary table, wherever feasible.
 - Note: in summaries of extreme values (i.e. when assessing the minimum/maximum on-treatment values), all post baseline values collected are used including those collected at unscheduled visits regardless of whether or not the value is closest to the scheduled visit date and appears in the corresponding visit-based summary.

Visit windows are described in Table 2.

Study Visit (Target Day)	Nominal Target Day	Study Visit Window (Days)		
		Lower	Upper	
Pre Screening Phase and Screening				
Phase ¹				
Visit 2 (Sereening)				
Open Label Phase			1^{1}	
OLP-Day 1	1	1	1	
OLP-Day 2 ²	2	2	2	
OLP-Day 3 ³	3	3	3	
End of OLP (24 hours or 48	2 or 3			
hours) ⁴				
End of Study Visit (OLP-Day 9) ⁵	9	4	16	
Randomized Treatment Phase				
Randomization (RTP-Day 1)	1	1	1	
Visit 6 (RTP-Day 2)	2	2	2	
Visit 7 (RTP-Day 5)	5	3	6	
Visit 8 (RTP-Day 8)	8	7	9	
Visit 9 (RTP-Day 12)	12	10	13	
Visit 10 (RTP-Day 15)	15	14	17	
Visit 11 (RTP-Day 19)	19	18	20	
Visit 12 (RTP-Day 22)	22	21	24	
Visit 13 (RTP-Day 26)	26	25	27	
Visit 14 (RTP-Day 29)	29	28	31	
End of Study Visit (RTP-Day 35) ⁶	35	32	43	

Table 2 Time windows for allocation of data to visits for statistical analysis

1. The screening phase lasts up to the date and time when the open label initial phase is initiated, i.e. date and time of the first dose.

2. Potassium is measured predose and 1 hour post dose. The predose measure is considered as the 24-hour measurement for all analyses. Patients who achieve normokalemia at 24 hours will proceed to the Randomization (RTP-Day 1) visit.

3. Potassium is measured predose and this measure is considered as the 48-hour measurement for all analyses.

4. End of OLP (24 hours or 48 hours) the latest treatment day of open label initial phase only for patients who complete 24 hours or 48 hours OLP treatment.

5. End of Study Visit (OLP-Day 9) in open label initial phase only for patients NOT entering the 28-day randomized treatment study phase and occurs 7±1 day after the last administration of IP.

6. End of Study Visit (RTP-Day 35) occurs 7±1 day after last planned administration of IP in RTP.

